### **Background, Rationale and Context**

Intravenous lidocaine is routinely given through the IV prior to injection of propofol to reduce the amount of pain during propofol injection. We want to study if giving the lidocaine through the IV while the forearm with the IV has a tourniquet applied to it to prevent “washing out” of the lidocaine prior to propofol injection helps reduce propofol injection pain.

### **Objectives**

We expect that tourniquet lidocaine will be superior to straight non-tourniquet lidocaine in reducing propofol injection pain. We also want to determine the association of tourniquet duration on reduction of pain with propofol administration. Small studies indicate that 60 seconds of tourniquet lidocaine is superior to 30 seconds or less of tourniquet duration or mixed lidocaine/propofol for injection. We suspect many clinicians do not use the 60-second tourniquet technique due to the extra time involved but hypothesize that a more practical application by applying the tourniquet as soon as the patient is positioned on the operating table will not only be more widely adopted by clinicians as it does not cause delay but also provide the necessary amount of time for benefit from the tourniquet. We plan to record the time from tourniquet application to start of propofol administration, which we predict will be at least 60 seconds, and see if there is a correlation between duration of venous stasis of IV lidocaine and pain benefit.

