### **Subjects selection criteria • Inclusion Criteria**

Any patient aged  $\geq 18$  years scheduled to receive propofol as part of their sedation or anesthetic.

- **Exclusion Criteria**

Since children (age < 18 years) frequently receive induction of anesthesia by mask, they will be excluded.

Any patient receiving pre-medications prior to their sedation that could alter their recall or perception of the pain such as fentanyl or midazolam.

- **Sample Size**

We estimate that 25 subjects in each of the two groups will be required to test the hypothesis based on prior studies.

**Interventions and Interactions** •

There will be two groups: ○ Group 1: 50mg of 2% lidocaine given just prior to the propofol dose through the IV line.

○ Group 2: 50mg of 2% lidocaine given IV with venous occlusion applied when the patient is positioned on the operating room table and timed until the onset of propofol administration. The tourniquet will either be a latex free tourniquet or McKesson Quick Release tourniquet applied to the forearm 10cm distal to the elbow joint in the tourniquet group. Venous stasis will be confirmed with cessation of flow from hanging IV fluid.

- For both groups, no premedication shall be given, which is the normal practice for these procedures. Study procedures will involve a 20 gauge intravenous (IV) catheter placed in a vein distal to the mid forearm. Venous occlusion will be achieved by either a latex free tourniquet or McKesson Quick Release tourniquet applied to the forearm 10cm distal to the elbow joint. Tourniquet pressure will be somewhat variable but sufficient to cause venous stasis as confirmed by no flow of hanging IV fluid. Injections will be delivered at roughly 1 ml/sec.
- For studies involving interactions the survey, questionnaire or method of observation should be described.
  - Please see Data Collection Form Attached

- The time required should occur within their usual anesthetic parameters and should not delay their procedure nor increase the duration of anesthesia significantly.

- Table illustrating the schedule of events in the study:

Day prior to the procedure	Describe study to the patient by telephone
Day of procedure: holding area	Consent patient for
Day of procedure: holding area	Randomly assign patient to one of two groups

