**Outcome Measures**

1. Self-described discomfort level using 4-point verbal pain scale (None, mild, moderate, severe)

2. Observer-graded discomfort level (Nonverbal vocal complaints, verbal vocal complaints, facial grimace/winces, and restlessness/withdrawal)
3. Post-procedure recall of discomfort using 4-point verbal pain scale (same as #1)

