### **Analytical Plan**

We will analyze results initially using descriptive statistics. Comparison between groups will be done using chi square tests for proportions, and t-tests or ANOVA procedures for continuous variables. Regression analysis will be performed to identify independent outcome predictors. Other inferential statistical analysis will be conducted as appropriate.

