**Appendix**

**Intravenous Lidocaine to Reduce Propofol Injection Pain:  
A Comparison of Two Methods**

MRN: \_\_\_\_\_

Date: \_\_\_\_\_

Observer: \_\_\_\_\_

PMH:	Chronic Pain Syndrome:	Y/N
	Daily use of Opioids:	
Y/ N		

Group (check one):             A (no tourniquet)             B (tourniquet)

Self-described discomfort level during injection using 4-point verbal pain scale:

- None
- Mild
- Moderate
- Severe

Investigator Assessments:

1) Induction Discomfort Scale (during injection and within 5 seconds after injection)

Grimace

IV forearm withdrawal

Moaning

Verbal statement of discomfort (“it hurts”, etc.)

2) Post-Procedure Discomfort Scale (in Recovery Area just prior to discharge).

I recall \_\_\_\_\_ discomfort in my IV arm while I went to sleep:

No

Mild

Moderate

Severe

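### The hypothesis that early tourniquet placement causes no delay has no comparator, because a time to propofol is planned only in the tourniquet group

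*Combined protocol and SAP*

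**What the plan says.** The Objectives section suspects that clinicians avoid the 60-second tourniquet technique because of the extra time. It then hypothesises that applying the tourniquet once the patient is on the table "will not only be more widely adopted by clinicians as it does not cause delay" and will also allow enough tourniquet time for benefit.

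The timing it plans is this: "We plan to record the time from tourniquet application to start of propofol administration". The predicted value is at least 60 seconds.

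Under Interventions and Interactions, the Group 2 tourniquet is "applied when the patient is positioned on the operating room table and timed until the onset of propofol administration". Group 1 receives "50mg of 2% lidocaine given just prior to the propofol dose through the IV line", with no start point and no recorded interval.

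Outcome Measures lists three discomfort outcomes, beginning with "Self-described discomfort level using 4-point verbal pain scale", and no time outcome. The Analytical Plan is generic (for example "t-tests or ANOVA procedures for continuous variables") and names no delay comparison, reference time or margin. The data form in the Appendix has discomfort items such as "Induction Discomfort Scale (during injection and within 5 seconds after injection" but no field for a clock time or a duration in either group.

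**The concern.** The hypothesis has two halves: the method adds no delay, which is why clinicians would adopt it, and it still gives enough tourniquet time. The second half has a measurement attached; the first has none.

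Delay is a difference between the time taken with the method and the time taken without it. The plan collects only the first of these. The control group that could supply the second is already randomised but is not timed.

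At stake is the practical argument that sets this technique apart from the 60-second one. If the report went on to say that the method adds no time, no data from the trial would support it. Clock times not noted during the procedure may not be recoverable afterwards.

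**Working it through.** **1. The quantity needed and what is planned.** Let T1 and T2 be the mean times from positioning to the start of propofol in Groups 1 and 2.

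- Delay attributable to the method = T2 − T1.
- T2: approximated by the planned tourniquet-to-propofol interval, because the tourniquet goes on at positioning (Objectives; Interventions and Interactions).
- T1: not planned anywhere. The planned interval cannot exist without a tourniquet, and the documents give no benchmark for the usual positioning-to-propofol time.

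**2. What a Group 2 result would show.** Suppose T2 is 60 s, the lower end of the plan's prediction. If routine preparation also takes 60 s, the delay is 60 − 60 = 0 s. If the control group would have been ready almost at once, the delay approaches 60 − 0 = 60 s. Both fit the same Group 2 data. Group 2 alone can answer whether the interval reaches 60 seconds, but not whether time was added.

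**3. The plan's own figure.** The only design figure is 25 per group, said to rest on prior studies. It cannot be reproduced, because alpha, power, effect size and variability are not stated. The point does not depend on it; it serves below only as the number of patients available.

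**4. Precision if both groups were timed.** Assume 25 analysed per group and a common SD, which the documents do not give.

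- 95% CI half-width = t(0.975, 48) × SD × √(2/25) = 2.011 × 0.2828 × SD ≈ 0.57 SD.
- Smallest margin that could be excluded with 80% power at one-sided 0.025, if the true difference is zero (normal approximation) = (1.960 + 0.842) × 0.2828 × SD ≈ 0.79 SD.

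| Assumed SD (s) | 95% CI half-width (s) | Smallest excludable margin (s) |
|---|---|---|
| 20 | 11.4 | 16 |
| 30 | 17.1 | 24 |
| 60 | 34.1 | 48 |
| 120 | 68.2 | 95 |

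At an SD of 20 or 30 s the comparison would be informative about delays well under a minute. At 120 s it could not reliably exclude a one-minute delay. These figures describe how well the added comparison would perform, not the size of a defect in the present plan.

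**The case against.** The strongest reply is that no-delay is not an endpoint. The Objectives section has two working aims: superiority on pain, and the association between tourniquet duration and pain. The no-delay clause is the reason offered for wider adoption, which this trial could not measure under any timing scheme. No section commits the investigators to concluding that there is no delay. This largely stands and makes the point minor. It does not remove it, because the clause sits inside a stated hypothesis and half of that hypothesis has no data behind it.

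Three stronger readings are tempting, and the documents do not support them.

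- A reader might infer that the claim is made twice, because Interventions and Interactions says the time required "should not delay their procedure nor increase the duration of anesthesia significantly". That sentence follows the description of the questionnaire and most naturally concerns the time burden of taking part in the study. It is not a statement about the technique against control.
- A reader might take 60 s as the natural margin. The Objectives section gives 60 seconds as a tourniquet duration and never quantifies the extra time. If the extra time were about 60 s, a 60 s margin would allow a no-delay claim for a method costing nearly as much time as the one it is meant to improve on.
- A reader might infer that 25 per group is certainly enough to settle the matter. That depends on an unknown SD.

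**Conclusion.** The point holds as a minor, secondary one. As planned, the no-delay part of the hypothesis has no comparator, no outcome, no analysis and no data field. The randomised pain comparison is untouched, and the 60-second prediction can be checked in Group 2 alone, provided the interval is written down; the present form has no place even for that.

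The conclusion rests on reading the sections together and on no numerical assumption. Only the precision of the remedy does: a 95% CI half-width of about 0.57 SD, from about 11 s at an SD of 20 s to about 68 s at an SD of 120 s. A reader should not infer that any planned inference is biased or underpowered because of this gap.

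**What to change.** - **Data form (Appendix).** Add the time of positioning on the table and the time propofol starts, for both groups, and the time of tourniquet application for Group 2. The last entry also supports the stated aim of relating tourniquet duration to pain.
- **Analytical Plan.** Report the between-group difference in mean positioning-to-propofol time with a 95% CI, as a descriptive secondary result.
- **If a no-delay claim is intended.** Before data collection, state a margin clearly shorter than the extra time of the 60-second technique, with its justification, and claim no delay only if the upper confidence limit lies below it.
- **If not.** Word no-delay in the Objectives as an untested rationale and do not conclude it in the report.

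The cost is two clock times per patient in Group 1, three in Group 2, and one more analysis. The precision of that analysis cannot be promised in advance, because the documents give no SD.

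### The plan times tourniquet to propofol, which is only an upper bound on the lidocaine stasis it wants to correlate with pain, and the form has no field for any time

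*Combined protocol and SAP*

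**What the plan says.** The Objectives section words the duration question in two ways. The first is "We also want to determine the association of tourniquet duration on reduction of pain with propofol administration". The second follows the statement "We plan to record the time from tourniquet application to start of propofol administration": the protocol predicts that this interval will be 60 seconds or longer, and will look for a "correlation between duration of venous stasis of IV lidocaine and pain benefit".

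The Background describes the technique as "giving the lidocaine through the IV while the forearm with the IV has a tourniquet applied to it", so the tourniquet goes on before the lidocaine. Under Interventions and Interactions, Group 2 has "venous occlusion applied when the patient is positioned on the operating room table and timed until the onset of propofol administration". Group 1 has a stated moment for its lidocaine: "50mg of 2% lidocaine given just prior to the propofol dose through the IV line". Group 2 has none. The same section adds "Venous stasis will be confirmed with cessation of flow from hanging IV fluid", without saying whether this check comes before or after the lidocaine, and "Injections will be delivered at roughly 1 ml/sec".

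For data capture, that section refers to the attached form. The form in the Appendix has fields for record number, date, observer, pain history, group, self-reported discomfort, observed signs and later recall. Its only references to time say when an assessment is made; none is a blank to fill in. The Analytical Plan mentions regression in general terms and names no duration variable.

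**The concern.** Stasis of lidocaine cannot begin before the lidocaine is in the vein, and it ends when the tourniquet is released. The planned clock starts at tourniquet application and stops at propofol, so it includes any wait before the injection and any time after an early release. If those components vary between patients, they add noise to the exposure and may dilute its correlation with pain towards zero.

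The 60-second prediction is affected too. The rationale cites 60 seconds of tourniquet lidocaine, and a tourniquet-to-propofol time of 60 s does not show that this was achieved.

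The form raises a simpler problem. Used as printed, it would not capture even the interval that the text promises, and no section names another source from which the times could be recovered.

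**Working it through.** **Decomposition.** Let T be tourniquet application to propofol start (the planned interval), D tourniquet application to lidocaine injection, and E tourniquet release to propofol start (zero if the tourniquet is still on). Pre-propofol lidocaine stasis is

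S = T − D − E, with D ≥ 0 and E ≥ 0, so S ≤ T.

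Equality requires lidocaine at the moment of application and no release before propofol. The protocol neither fixes nor records D or E.

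**Range from the protocol's own figures.** 2% lidocaine is 20 mg/mL, so 50 mg is 50 / 20 = 2.5 mL. At roughly 1 mL/s the injection takes about 2.5 s. With T = 60 s, stasis counted from the end of injection is at most 60 − 2.5 = 57.5 s and can be close to 0. The injection itself is short enough that a single clock time describes it. With E = 0 and assumed D of 15, 30 or 45 s, time from lidocaine to propofol is 45, 30 or 15 s.

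**Dilution (illustration only).** The documents give no gap, no spread of stasis times (dwell), no correlation and no pain distribution, so every input except n is assumed. With E = 0 and D independent of both S and pain, the latent correlation with T is

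r_T = r_S / √(1 + var(D)/var(S)).

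For r_S = 0.50 and a dwell SD of 30 s, a gap SD of 15 s gives 0.50 / √1.25 = 0.447, and a gap SD of 30 s gives 0.50 / √2 = 0.354.

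Power was simulated for n = 25 (the planned Group 2 size), with a two-sided 5% Spearman test. A latent normal outcome was cut to four levels (none/mild/moderate/severe). There were 20,000 trials per cell, with a Monte Carlo SE of about 0.35 points. Type I error was 4.8 to 5.0%.

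| Assumed pain distribution (%) | Gap SD 0 s | 5 s | 10 s | 15 s | 30 s |
|---|---|---|---|---|---|
| 50/25/15/10 | 58.9% | 58.6% | 54.1% | 48.6% | 32.2% |
| 70/15/10/5 | 49.2% | 48.2% | 44.7% | 39.9% | 26.7% |
| 80/10/7/3 | 40.1% | 39.3% | 36.9% | 32.8% | 21.6% |

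Loss against perfect timing: at most 1 point at 5 s, 3 to 5 at 10 s, 7 to 10 at 15 s, and 19 to 27 at 30 s.

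**Sensitivity to dwell SD (r_S = 0.50).** At a dwell SD of 20 s, power at gap SDs of 15 and 30 s is 40.5% and 21.1% (50% reporting none), or 33.0% and 17.4% (70% none). At a dwell SD of 40 s it is 53.1% and 39.9%, or 44.0% and 33.4%.

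**Perfect timing, weaker correlation.** Across the three distributions, power is 39.7%, 33.1% and 27.0% at r_S = 0.40, and 23.5%, 19.9% and 16.2% at 0.30. The four-level scale is itself costly: the Fisher-z approximation for a continuous outcome gives 73.1% at r = 0.50 and n = 25, which is 14 to 33 points above the first column of the table.

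**The case against.** The strongest reply is that the protocol may intend one quantity under two names. The Objectives section also states the question as one of tourniquet duration, and the planned interval is that exposure provided the tourniquet stays on until propofol. The stasis phrase comes in the same sentence as the interval and may be a loose label for it. The Group 2 description can be read as lidocaine and occlusion given together, with a gap of seconds. Nothing suggests early release, and injecting just before propofol would defeat the stated rationale. All of this is fair. It makes the mismatch an ambiguity that the plan leaves open, not proof that the gap is large.

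On size, the loss of 19 to 27 points needs a gap as variable as the dwell, which nothing in the protocol suggests, and one independent of it. With gap and dwell positively correlated (assumed 0.5), the loss at a 30 s gap SD is about 10 to 14 points. Sample size and the coarse scale limit this analysis more than a short gap would. That stands, and it limits the severity.

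The missing field may be clerical, since the text commits to timing in two places. The form is also attached under a prompt about questionnaires and observation, so it need not be the whole data record. But it is the only instrument shown. Without injection and release times, nobody can establish afterwards whether the gap was trivial.

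**Conclusion.** The concern holds and should be fixed. Two parts rest on the text alone: the planned interval is an upper bound on pre-propofol lidocaine stasis, and the form has no field for any time. The size of the harm is not known. It is nil for a constant gap with no early release, small for a short gap, and material only if the gap or early release varies by an amount comparable with the dwell. The power figures rest on assumed correlations, SDs and pain distributions and only illustrate the scale.

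What is at stake is a secondary correlation in about 25 patients, exploratory under any timing scheme, together with the interpretation of the 60-second prediction. The randomised tourniquet-versus-none comparison is not affected.

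**What to change.** For Group 2, add four clock times to the data collection form: tourniquet on, lidocaine injected, tourniquet released, propofol start. Then state in the Analytical Plan:

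- Tourniquet application to propofol start is kept for the 60-second prediction.
- The exposure for the stasis correlation is lidocaine injection to tourniquet release, or to propofol start if the tourniquet is still on.
- The correlation is analysed within Group 2 by a rank or ordinal method on the four-point scale, with a confidence interval, and labelled exploratory.
- The observed tourniquet-to-lidocaine gap is reported (median and range), so readers can see whether the two exposures differ.

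The first two times and the choice of exposure address the stasis wording; the release time covers the case where the tourniquet comes off before propofol. None of this changes clinical timing.

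The cost is four lines on a one-page form and one sentence in the Analytical Plan. The drawback is extra recording in one arm: release and propofol start may fall close to the moment when the observer grades discomfort, so the added timing must not distract from that assessment.

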### **Methods and Measures**

#### **Design**

This will be conducted as a randomized controlled trial of two methods of administering lidocaine prior to propofol injection.

#### **Setting**

The study setting is located within North Carolina Baptist Health, an academic medical center, in the Endoscopy Suite where 10-30 patients per day are scheduled to receive propofol as part of their sedation or anesthetic.

### **Subjects selection criteria • Inclusion Criteria**

Any patient aged  $\geq 18$  years scheduled to receive propofol as part of their sedation or anesthetic.

- **Exclusion Criteria**

Since children (age < 18 years) frequently receive induction of anesthesia by mask, they will be excluded.

Any patient receiving pre-medications prior to their sedation that could alter their recall or perception of the pain such as fentanyl or midazolam.

- **Sample Size**

We estimate that 25 subjects in each of the two groups will be required to test the hypothesis based on prior studies.

**Interventions and Interactions** •

There will be two groups: ○ Group 1: 50mg of 2% lidocaine given just prior to the propofol dose through the IV line.

○ Group 2: 50mg of 2% lidocaine given IV with venous occlusion applied when the patient is positioned on the operating room table and timed until the onset of propofol administration. The tourniquet will either be a latex free tourniquet or McKesson Quick Release tourniquet applied to the forearm 10cm distal to the elbow joint in the tourniquet group. Venous stasis will be confirmed with cessation of flow from hanging IV fluid.

- For both groups, no premedication shall be given, which is the normal practice for these procedures. Study procedures will involve a 20 gauge intravenous (IV) catheter placed in a vein distal to the mid forearm. Venous occlusion will be achieved by either a latex free tourniquet or McKesson Quick Release tourniquet applied to the forearm 10cm distal to the elbow joint. Tourniquet pressure will be somewhat variable but sufficient to cause venous stasis as confirmed by no flow of hanging IV fluid. Injections will be delivered at roughly 1 ml/sec.
- For studies involving interactions the survey, questionnaire or method of observation should be described.
  - Please see Data Collection Form Attached

- The time required should occur within their usual anesthetic parameters and should not delay their procedure nor increase the duration of anesthesia significantly.

- Table illustrating the schedule of events in the study:

Day prior to the procedure	Describe study to the patient by telephone
Day of procedure: holding area	Consent patient for
Day of procedure: holding area	Randomly assign patient to one of two groups
Day of procedure: procedure area	Accompany patient to the operating or procedure room, perform instructions from the group they are assigned to while noting outcome measures such as self-described discomfort and observer graded discomfort
Day of procedure: recovery area	Revisit patient in recovery to determine post-procedure recall of discomfort
Post-study period	Analyze data

